### **3.7 Treatment assignment and treatment groups**

This is an open label, single arm study.

Treatment group at the completion of PA0008 (presented as ‘BKZ 160mg’ or ‘BKZ 320mg’) and an overall ‘BKZ Total’ column will be used to summarize data in PA0009.

The endpoints assessing maintenance of ACR and PASI response over time will be summarized by treatment sequence across PA0008 and PA0009. Treatment sequences take the form ‘A/B/C’, where A is the treatment in the first 12 weeks of PA0008, B is the treatment from Week 12 to Week 48 of PA0008, and C is the treatment in PA0009. The seven planned treatment sequences are as follows:

- Placebo/BKZ 160mg/BKZ 160mg.
- Placebo/BKZ 320mg/BKZ 160mg.
- BKZ 16mg/BKZ 160mg/BKZ 160mg.
- BKZ 16mg/BKZ 320mg/BKZ 160mg.
- BKZ 160mg loading dose (LD)/BKZ 160mg/BKZ 160mg.
- BKZ 160mg/BKZ 160mg/BKZ 160mg.
- BKZ 320mg/BKZ 320mg/BKZ 160mg.

For safety summaries the following will be presented:

- Safety summaries including PA0009 data only will be presented by treatment group at the completion of PA0008 and overall.
- Safety summaries including data from both PA0008 and PA0009 combined will be presented for 'BKZ 160mg', 'BKZ 320mg', and 'BKZ Total'. The assignment of each of the sequences to the columns in this table is presented in [Table 3-2](#).
  - The 'BKZ 160mg' treatment column in these tables will include subjects in both the BKZ 160mgLD and BKZ 160mg treatment groups.
  - For each column, only those periods for which the specified treatment is received will contribute to the summary ie, for sequence BKZ 16mg/BKZ 320mg/BKZ 160mg, the 16mg period will contribute to the BKZ Total column only, the BKZ 320mg period will contribute to the BKZ 320mg column and the BKZ Total column only, and the BKZ 160mg period will contribute to the BKZ 160mg column and the BKZ Total column only.

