In addition, the ADAb status will be further classified on a subject level as outlined below:

- **Pre ADAb negative – treatment emergent ADAb negative (Category 1):**
  - Considering PA0009 data only (Category 1a): includes subjects who are ADAb negative at PA0008 Baseline and ADAb negative at all sampling points in PA0009 (including SFU).
  - Considering PA0008 and PA0009 data (Category 1b): includes subjects who are negative at PA0008 Baseline and ADAb negative at all sampling points in PA0008 and PA0009 (including PA0009 SFU).
- **Pre ADAb negative – treatment emergent ADAb positive (Category 2):**

- Considering PA0009 data only (Category 2a): Includes subjects who are negative at PA0008 Baseline and ADA b positive at any sampling point post treatment in PA0009 (up to and including SFU and including the PA0009 EV). This group also includes subjects who have a missing pre-treatment sample (either missing or insufficient volume) at PA0008 Baseline with one or more ADA b positive samples in PA0009.
- Considering PA0008 and PA0009 data (Category 2b): Includes subjects who are negative at PA0008 Baseline and ADA b positive at any sampling point post treatment in PA0008 (up to and including PA0009 SFU). This group also includes subjects who have a missing pre-treatment sample (either missing or insufficient volume) at PA0008 Baseline with one or more ADA b positive samples in PA0008 or PA0009.
- **Pre ADA b positive – treatment emergent reduced ADA b (Category 3):**
  - Considering PA0009 data only (Category 3a): Includes subjects who are positive at PA0008 Baseline, and ADA b negative at all sampling points in PA0009 (including SFU).
  - Considering PA0008 and PA0009 data (Category 3b): Includes subjects who are positive at PA0008 Baseline, and ADA b negative at all sampling points in PA0008 and PA0009 (including SFU).
- **Pre ADA b positive – treatment emergent unaffected ADA b positive (Category 4):**
  - Considering PA0009 data only (Category 4a): Includes subjects who are positive at PA0008 Baseline and are positive at any sampling point in PA0009 (including SFU) with titer values of the same magnitude as PA0008 Baseline (ie, less than a predefined fold increase from the PA0008 Baseline value defined within the validation of the assay).

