  - Considering PA0008 and PA0009 data (Category 8b): Includes subjects who are pre ADA b negative – treatment emergent ADA b positive (Category 2b) and pre ADA b positive – treatment boosted ADA b positive (Category 5b).
- **Total pre ADA b positive (Category 8 [Categories 3, 4, 5 and 6 combined]):** Subjects that are tested ADA b positive at PA0008 Baseline.
- **Missing (Category 9):**
  - Considering PA0009 data only (Category 9a): Includes subjects who have a missing or negative pre-treatment sample at PA0008 Baseline and some PA0009 samples are missing, while other PA0009 samples are ADA b negative.
  - Considering PA0008 and PA0009 data (Category 9b): Includes subjects who have a missing or negative pre-treatment sample at PA0008 Baseline and some PA0008 or PA0009 samples are missing, while other PA0008 and PA0009 samples are all ADA b negative.

The following summaries, figures and listings will be produced:

- Summary tables displaying the number and percentage of subjects with a positive ADA b status at each PA0009 visit and at any visit by treatment group at completion of PA0008. Two tables will be presented:
  - Considering ADA b status in PA0009 only
  - Considering ADA b status in PA0008 and PA0009 (this table will include only the overall summary visits as detailed below).

For the overall summary at any visit 2 summaries will be presented as follows (all summaries exclude data obtained at PA0008 Baseline):

- PA0009 data only: Including any visit during the PA0009 treatment period (as defined in [Section 3.2.2](#)). Thus, this summary will exclude data obtained at the SFU visit and will include data obtained at the PA0009 EV.
- PA0009 data only: Including any visit during PA0009. Thus, this summary will include both data obtained at the SFU visit and at the PA0009 EV.
- PA0008 and PA0009 data: Including any visit during the PA0008 and PA0009 treatment period. Thus, this summary will exclude data obtained at the PA0009 SFU visit.
- PA0008 and PA0009 data: Including any visit during PA0008 and PA0009. Thus, this summary will include data obtained at the PA0009 SFU visit.
- Summary tables (by treatment at completion of PA0008) of the time point of the first occurrence of ADA b treatment-emergent positivity during PA0009, including the PA0009 EV and the SFU visit. This summary will include the following categories:
  - Category 2: Pre ADA b negative – treatment-emergent ADA b positive

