  - Category 5: Pre ADA b positive – treatment-boosted ADA b positive

The table will summarize the number and percentage of subjects who are either treatment-emergent ADA b positive or treatment-boosted ADA b positive for the first time at the specified time point in PA0009 and will include the cumulative number and percentage of subjects with treatment-emergent ADA b positive results at each time point.

The table will be repeated considering ADA b status at each visit in both PA0008 and PA0009 and will therefore display all visits in both PA0008 and PA0009.

An additional table will be presented considering ADA b status at each visit in both PA0008 and PA0009, and will be presented by treatment at randomization in PA0008.

- Summary tables displaying the number and percentage of subjects in each of the ADA b categories as defined above by treatment at completion of PA0008. Two tables will be presented:
  - Considering data from PA0009 only
  - Considering data from PA0008 and PA0009
- The time to achieving treatment-emergent ADA b positivity in PA0009, separated by treatment group at completion of PA0008, will be graphically presented. Subjects will be considered to have an event at the time point at which treatment-emergent ADA b positivity is first achieved. The plot will display the cumulative percentage of subjects with treatment-emergent positivity and will include the following categories (4 lines per plot):
  - Category 2: Pre ADA b negative – treatment-emergent ADA b positive
  - Category 5: Pre ADA b positive – treatment-boosted ADA b positive
    - Category 2 and Category 5 subjects will be combined in 1 group (2 lines per plot) if the percentage of subjects in each treatment group in Category 5 is <10%.

The figure will be repeated considering data from both PA0008 and PA0009 and will therefore display all visits in both PA0008 and PA0009.

In the event that  $\geq 10\%$  of subjects in either treatment group are classified as Category 5 the figure will be presented by treatment and ADA b status (4 lines per plot). This will be implemented for both plots (considering only PA0009 and considering data from both PA0008 and PA0009).

An additional figure will be presented considering data from both PA0008 and PA0009, and will be presented by treatment at randomization in PA0008 (for this figure the 160mgLD and 160mg treatments will be pooled). This figure will be presented as follows:

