- Action taken with IMP: dose not changed, dose reduced, dose increased, drug temporarily, interrupted, drug permanently withdrawn or not applicable.
- Outcome: resolving, not resolved, resolved, resolved with sequelae, worsened, fatal or unknown.

AEs (including SAEs) are characterized as either non-treatment-emergent or treatment emergent according to the following criteria:

- Non-treatment emergent AEs are those with onset date after a 140-day period after the end date of study medication.
  - Any AE occurring more than 140 days after the last administration of study medication in PA0008 and prior to the first administration of study medication in PA0009 will also be considered as non-treatment emergent, and will therefore be excluded from the summary tables. Such events will be included in the listings.
- TEAEs are those with onset date on or after the start date of study medication in PA0009.
- Events that were ongoing at the end of PA0008 will have their treatment-emergent status taken from the PA0008 database.

For all AEs the following variables will be calculated (see [Section 10.2.1](#)):

- Duration.
- Time since first bimekizumab dose.
- Time since last/latest bimekizumab dose.

AE summaries will, in general, include only events with onset on or after the start date of study treatment in PA0009. Certain displays will be repeated including all AEs in PA0008 (with the exception of those with onset during placebo treatment) and PA0009 as outlined below. These displays will include only subjects from PA0008 who were enrolled in PA0009.

In general, the attributes of these events (for AEs that started and were resolved in PA0008) will be taken from the PA0008 database. However, the identification of Safety Topics of Interest will be made across all events in PA0008 and PA0009 using the criteria defined in this SAP.

For events which were ongoing at the end of PA0008, the following rules will be implemented:

- Onset date (and derived variables) will be taken from the PA0008 database
- End date, outcome, actions taken and seriousness will be taken from the PA0009 database.
- In order to ensure that AEs are not duplicated in the outputs these will be merged across the studies by Subject ID, verbatim term (AETERM), dictionary-derived term (AEDECOD), start date (AESTDTC), relationship (AEREL) and severity (AESEV) to create one record for the specific event.

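### The combined PA0008+PA0009 antibody categories have no rule for the 12-week placebo phase, so a positive before any bimekizumab can be classed as treatment-emergent

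*SAP*

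**What the plan says.** SAP 3.7 writes each treatment sequence as A/B/C, "where A is the treatment in the first 12 weeks of PA0008". Two of the seven sequences begin on placebo: "Placebo/BKZ 160mg/BKZ 160mg" and "Placebo/BKZ 320mg/BKZ 160mg".

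SAP 9.2 classifies each subject's antibody (ADAb) status twice, once on PA0009 data (the 'a' categories) and once on both studies together (the 'b' categories). PA0008 Baseline is the pre-treatment sample throughout. In the combined version:

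- **1b (negative throughout)** needs a negative at Baseline and at every sampling point in both studies.
- **2b (treatment-emergent positive)** takes subjects who are Baseline-negative and "positive at any sampling point post treatment in PA0008 (up to and including PA0009 SFU". If the Baseline sample is missing or insufficient, one positive anywhere in either study is enough, with no timing condition.
- **5b (boosted)** takes Baseline-positive subjects with a more than 3-fold titer rise at a post-treatment point in either study. If no titers are available to judge, the subject defaults to boosted.
- The **treatment-emergent total** adds Categories 2 and 5.

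The combined first-occurrence table and time-to-positivity figure show all PA0008 visits, grouped by treatment at completion of PA0008. There is also a table by randomized treatment, and a matching figure: "An additional figure will be presented considering data from both PA0008 and PA0009, and will be presented by treatment at randomization in PA0008".

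Safety is handled differently. Under SAP 10.2 the combined adverse event displays take PA0008 events "with the exception of those with onset during placebo treatment", and Table 10-2 in SAP 10.1 starts total exposure at the first bimekizumab dose.

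**The concern.** An antibody positive found before a subject has had any bimekizumab cannot have been induced by it. It is either pre-existing reactivity or an assay false positive. Assessing immunogenicity is a stated objective (Protocol 3.3, SAP 2.1.3), and the combined outputs are the ones that follow subjects from the start of PA0008. If placebo-phase positives count, combined treatment-emergent incidence mixes unexposed positives with drug-induced ones. Grouping by treatment at completion of PA0008 also places placebo-start subjects on the same curve as subjects who began bimekizumab 12 weeks sooner. The SAP sets placebo time aside for adverse events, and SAP 3.10 gives no reason for treating antibodies differently.

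**Working it through.** **1. The plan's own exposure figure.** SAP 13.1.2 says the PA0009 entry visit follows 36 or 48 weeks of bimekizumab. Entry is PA0008 Week 48, so placebo-start subjects have 48 − 12 = 36 weeks and active-start subjects 48 − 0 = 48. The figure is reproduced. For the two placebo-start sequences the PA0008 axis therefore contains 12 weeks without bimekizumab. That is 12/(48 + 104) = 12/152 = 7.9% of the span to PA0009 Week 104, or 12/(48 + 120) = 12/168 = 7.1% of the span to safety follow-up.

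**2. Where the subject lands.** Take a placebo-start subject with a negative Baseline, one positive in the placebo phase, every later sample negative and none missing.

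- 1b fails, because not every PA0008 sample is negative.
- 3b to 6b fail, because each needs a positive Baseline.
- 9b fails, because it needs missing samples and no positives.
- 2b is the only category left, and it feeds the treatment-emergent total.

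With a missing Baseline the subject again lands in 2b, through the branch that has no timing condition. A Baseline-positive subject whose titer rises more than 3-fold during placebo lands in 5b by the same logic.

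If samples before the first bimekizumab dose are not counted as post-treatment, and the last of them is negative, the first subject moves to 1b. If the positive is itself the last sample before that dose, the subject is pre-treatment positive and moves to 3b.

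**3. Timing.** A placebo-start subject first positive at PA0008 Week *w*, after the switch, is shown at *w* but has had *w* − 12 weeks since starting bimekizumab. The displacement is 12 weeks at every such visit. It does not apply to a subject whose first positive is in the placebo phase; that event is shown before exposure has begun.

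**4. Possible size.** The documents give no PA0008 arm sizes, no PA0008 antibody sampling schedule and no false-positive rate after confirmation. The following inputs are assumptions:

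- *n* = 30 or 40 placebo-start subjects who rolled over. Forty is 200/5 if the five randomized groups were equal; 30 allows for some not continuing.
- *k* = 1, 2 or 4 placebo-phase samples per subject.
- *p* = confirmed false-positive rate per sample, from 0.05% up to 5%. The upper end is the screening-stage rate in SAP 9.2, used here as a ceiling.

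With independent samples, the expected number of subjects with at least one such positive is *n* × (1 − (1 − *p*)^*k*):

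| *n* | *p* | *k* = 1 | *k* = 2 | *k* = 4 |
|---|---|---|---|---|
| 30 | 0.05% | 0.015 | 0.03 | 0.06 |
| 30 | 1% | 0.30 | 0.60 | 1.18 |
| 40 | 1% | 0.40 | 0.80 | 1.58 |
| 40 | 5% | 2.00 | 3.90 | 7.42 |

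With *n* = 40 and *p* = 1%, the chance of at least one affected subject is 33% (*k* = 1) to 80% (*k* = 4). Some of these subjects might also turn positive later on drug. They would be 2b under either rule, and only their onset would be wrong.

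**The case against.** The best defense is that 'post treatment' is undefined in SAP 9.2 and appears only in Categories 2 and 5, so it might mean after bimekizumab. It is fair that the other reading is an inference. It is a strong one: SAP 3.2.1 counts placebo as PA0008 study medication, the pre-treatment sample is fixed at PA0008 Baseline, and the missing-Baseline branch of 2b lacks the phrase altogether. The narrower reading also leaves a gap, because the subject in step 2 would fit neither 2b nor 1b nor any other category. Either way the text needs changing. The time origin of the combined figure is likewise not stated in words; it follows from the display of all PA0008 visits.

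A second defense is that the extra table and figure by randomized treatment give the placebo-start group its own column and curve, and that subject-level listings are planned. This stands as mitigation. Those displays still use the same category definitions, and the outputs by treatment at completion of PA0008 are not corrected.

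Several stronger readings are tempting but not supported:

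- *All immunogenicity results are affected.* The PA0009-only categories and displays are not, since every subject has at least 36 weeks of bimekizumab by entry. Category 8 as written uses only the Baseline sample.
- *The any-visit summaries overstate treatment-emergent incidence.* They cover "PA0008 and PA0009 data: Including any visit during the PA0008 and PA0009 treatment period" but report positive status, not treatment-emergent status.
- *Unexposed person-time dilutes a rate.* These outputs are cumulative percentages by visit, with no person-time denominator.
- *Every placebo-start subject's onset is late.* Only those first positive after the switch are displaced. Placebo-phase positives pull apparent onset earlier, so the two effects oppose each other and the net direction is unknown.

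**Conclusion.** The point holds for Categories 2b and 5b, their total, and the combined first-occurrence table and time-to-positivity figure by treatment at completion of PA0008. As written, the rules class a placebo-phase positive as treatment-emergent and put placebo-start and active-start subjects on one visit axis although their exposure begins 12 weeks apart. The axis displacement follows from the design and does not depend on any assumed rate. The count of misclassified subjects does: it may be zero, is probably small, and cannot be fixed from the documents. The outputs are descriptive, so this should be corrected but does not threaten the study's main safety results.

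**What to change.** In SAP 9.2, for the combined outputs only:

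- Define 'post treatment' as after the first bimekizumab dose.
- For the two placebo-start sequences, take status and titer from the last available ADAb sample before that dose as the pre-treatment sample, falling back to PA0008 Baseline if there is no later one.
- Do not count placebo-phase samples as post-treatment in Categories 1b to 6b, the treatment-emergent total and 9b.
- Time the combined first-occurrence table and time-to-positivity figure from the first bimekizumab dose, in line with SAP 10.1 and 10.2.
- Check the wording of Category 8. It is defined both as the sum of Categories 3 to 6 and by positivity at PA0008 Baseline, and the two could differ for placebo-start subjects once the pre-treatment sample moves.

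The cost is SAP wording and some reprogramming, with no new samples. The downside is a small departure from SAP 3.3, which uses PA0008 Baseline without re-derivation, and from the program-wide antibody categories cited in SAP 13.1.2.

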## 10 SAFETY ANALYSES

AEs will be coded according to MedDRA.

AEs will be summarized by treatment group at completion of PA0008 and overall, by primary SOC, HLT, and PT in alphabetical order. This summary will include incidence, exposure-adjusted incidence rates (EAIRs) with associated 95% CIs, and exposure-adjusted event rates (EAERs) where the EAIR and EAER are expressed per 100 subject-years of exposure. Subject exposure at risk is defined in [Section 10.1](#).

Change from PA0009 Laboratory Baseline values in laboratory variables (except CRP) will be summarized descriptively by visit and by treatment group at completion of PA0008 and overall.

Change from PA0008 Baseline values in ECG and vital signs variables will be summarized descriptively by visit and by treatment group at completion of PA0008 and overall.

Safety variables will be reported for the SS. Key safety analyses will be repeated for both SS Sub-populations (see [Section 3.6.2](#)) and/or will include data from PA0008 for subjects who continued in to PA0009, as described below.

### 10.1 Extent of exposure

Study medication duration will be calculated for each of the following using the imputation rules in [Section 4.2.5](#) for partial treatment end dates:

- Total bimekizumab duration: Between the first dose of bimekizumab in PA0008 and last dose of bimekizumab in PA0009.
- Total duration on bimekizumab 160mg and 160mgLD combined (required for AE summaries only): Between the first dose of bimekizumab 160mgLD or 160mg and last dose of bimekizumab 160mg (in PA0008 or PA0009).
- Duration on bimekizumab 320mg: Between the first dose of bimekizumab 320mg in PA0008 and first dose of bimekizumab 160mg in PA0009 (calculated only for subjects who took bimekizumab 320mg in PA0008).
- Duration on bimekizumab 160mg in PA0009: Between the first and last dose of bimekizumab 160mg in PA0009.

The duration of exposure will be calculated as outlined in [Table 10-1](#).

**Table 10-1: Study medication duration**

Duration Category	Start Date	End Date	Study Medication Duration
Total BKZ duration	First dose of BKZ in PA0008	Last dose of BKZ in PA0009	End date – start date + 28 a
Total duration on BKZ 160mgLD and BKZ 160mg	First dose of BKZ 160mgLD or 160mg in PA0008 or PA0009	Last dose of BKZ 160mg in PA0009	End date – start date + 28 a

**Table 10-1: Study medication duration**

Duration Category	Start Date	End Date	Study Medication Duration
Duration on BKZ 320mg	First dose of BKZ 320mg in PA0008	First dose of BKZ 160mg in PA0009	End date – start date + 1
Duration on BKZ 160mg in PA0009	First dose of BKZ 160mg in PA0009	Last dose of BKZ 160mg in PA0009	End date – start date + 28 a
Subjects who died b	Start date for each option as above	Date of death	End date – start date + 1

BKZ=bimekizumab; LD=loading dose.

a 28 days refer to one half-life of BKZ.

b For subjects who died, the date of death will be used to replace the end date in the calculation of study medication duration only if the subject died within the dosing interval (ie, within 28 days following the last dose [not applicable for duration on BKZ 320mg]) or if the subject died before dosing in PA0009 (for duration on BKZ 320mg). If the subject died more than 28 days after the last dose of BKZ in PA0009 the study medication duration will be calculated using the dosing interval of 28 days.

The exposure time at risk will be calculated as outlined in [Table 10-2](#).

